As with inhaled drugs, venous anesthetics also act on the respiratory system. Propofol reduces the cross-sectional area of the upper airway, a reduction that has been shown to be maximum at the base of the tongue when sedative doses are used. Induction with this agent reduces the electromyographic activity of the genioglossus muscle⁶.

During the apnea period following general anesthesia induction, oxygen stores (O₂) are being consumed which may result in hypoxemia⁸. Oxyhemoglobin desaturation is faster in patients with reduced O₂ transport capacity, ie, those with reduced CRF, partial oxygen pressure (PaO₂), arterial oxygen content and cardiac output, or increased oxygen uptake (VO₂).)⁹.

General anesthesia appears as a major risk factor for mortality in pediatric surgical patients, and problems with airway management in patients with comorbidities appear to add life-threatening risk to this population¹⁰. Pediatric patients, in turn, have more frequent episodes of desaturation during induction (4-10%)^{5,8,11,12}. Children undergoing a greater number of tracheal intubation attempts, considered to have a difficult airway, are at greater risk of desaturation, which, if left untreated, naturally evolves to hypoxemia¹². The occurrence of this during airway manipulation in children may be accompanied by even more serious complications such as cardiopulmonary arrest (CRP) and death¹¹.

Decreasing oxyhemoglobin saturation to levels less than or equal to 95% induces changes in hemodynamic parameters such as systolic index [ratio of heart index (systolic volume x heart rate / body surface area) and heart rate], which indicates a reduction in blood pressure. heart function¹³.

Data from a five-year tertiary hospital study (12,158 surgeries) document respiratory events accounting for 29% of perioperative cardiac arrest in children. This share rises to more than half (56%) when analyzing anesthesia-related data. All CRP attributed exclusively to the anesthetic act were induction¹⁴.

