Frequency of complications: laryngospasm, hypoxemia, bradycardia, cardiopulmonary arrest, death;

Time to recover oxyhemoglobin saturation levels in pre-apnea pulse oximetry (Time 2);

Procedures, tests, techniques and exams

Performing Anesthesia:

Patients selected for the study will be admitted to the operating room and will receive regular monitoring (cardioscope, oximeter, noninvasive blood pressure and capnography).

Inhalation induction will be with 8% sevoflurane, 60.5% inspired oxygen fraction under fresh gas flow of 4l / min (2l oxygen and 2l compressed air) until loss of eyelid reflex. The anesthetic concentration will then be reduced to 4%. A face mask coupled to the anesthesia machine will be used, fixed to the patient through an elastic band.

After adequate ventilation is verified through the correct positioning of the face mask and capnography curve present, peripheral venous access with venous catheter number 20, 22 or 24G will be obtained for hydration and propofol infusion at a dose of 3.5mg / kg to induce apnea in patients in both groups.

CPAP Realization

Patients will be submitted soon after monitoring the technique described on the envelopes delivered at the entrance to the operating room.

In the CPAP group, it will be applied to the anesthesia device (Dräger Fabius GS) using a circular system. This system consists of two corrugated tubes coupled at one end to a Y-piece, connected to the patient's face mask, and at the other end to the anesthesia machine which, in addition to providing fresh gas flow, has a carbon dioxide absorber called lime. soda. The latter allows the system to be circulated by removing CO₂ from the air supplied to the patient, warms and humidifies the gas mixture. A pressure relief valve (pop-off valve), which prevents gas loss by the patient-device system when closed, is an integral part of the anesthesia device. It has several markings (0-70cmH₂O), is manually manipulated and can be open (0cmH₂O), ie without any pressure being supplied to the patient's airway or closed. In the closed position, there will be continuous positive pressure being delivered to the patient's airway. The pressure that will be used in this group will be 10cmH₂O.

In the Open System group, the system will remain with the valve in the open position, ie 0cmH₂O.

In both groups, patients will spontaneously ventilate from the outset with the technique defined at the time of allocation.

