After the apnea begins, the time will be timed and periodically (every 10 seconds), the oxyhemoglobin saturation through the pulse oximeter will be recorded for a maximum time limit of five minutes in order to catch a minimum saturation of 95% in both groups.

The entire anesthetic procedure will be attended by the anesthesiologist who accompanies the patient and will be at his discretion as soon as the study is over.

Procedures for data collection

Data Collection Instrument

Data will be collected using a standard, pre-coded form for data entry into the computer (Appendix 3). Information on categorical variables will be pre-coded and continuous variables will be expressed at their own numerical value and only at the time of analysis will the results of some of these be categorized.

These forms will be properly stored in specific file folders, before and after typing and analysis, under the responsibility of the researcher, who will fill them out at different times, before, during and after the surgical procedure.

Data collect

Data will be collected by an independent researcher who will be present in the operating room, fill out the form with patient identification data and study variables and will not interfere with the anesthetic procedure to be performed.

The time from the moment of cessation of respiratory movements and decay of the capnography curve will be timed. The measurement will take place until the pulse oximetry is recorded at 95%. Assisted ventilation will then be instituted (in the Open System group, the pop-off valve will be manually closed to 10cmH₂O). At this time, there will be a new timing of the time until pulse oximetry reading of the value of 100% or the value obtained immediately before the beginning of apnea.

Data Processing and Analysis

Data Processing

Typing in the specific database created in the excel program will be performed twice, at different times and by different people, obtaining at the end a listing to correct any typing errors, under the supervision of the researcher himself.

In case of inconsistencies or lack of data when the listings are reviewed, the corresponding archived forms will be consulted, according to the patient's registration number.

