The study will be registered in ClinicalTrials.gov and will not offer any additional risks or discomforts beyond those inherent to the anesthetic-surgical procedure itself, as well as no adverse effects that contraindicate the use of CPAP during induction have not been reported in the literature. In contrast, the few existing studies report respiratory improvement with the use of this intervention. All research procedures will be performed by trained and qualified professionals for both pediatric anesthesia and CPAP.

The informed consent form (Appendix 2) will provide the guardians with all information regarding the advantages and disadvantages of using both techniques; emphasize that no procedures no longer routinely performed by the team will be performed; It will include the right to refuse to participate in the study, as well as the guarantee of assistance to those who do not accept it, without compensation from the institution or from the researchers. They will undertake to publish the study, regardless of the results obtained.

Interest conflicts

This research will be free of conflict of interest, private or institutional. There will be no funding from the pharmaceutical industry or representatives of any research object used.

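### The statement that the study adds no risk is inconsistent with an induced apnea in both groups in which assisted ventilation waits for a 95% saturation reading

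*Combined protocol and SAP*

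**What the plan says.** Ethical aspects states that the study "will not offer any additional risks or discomforts beyond those inherent to the anesthetic-surgical procedure itself". The same section says the consent form will "emphasize that no procedures no longer routinely performed by the team will be performed". That wording is garbled but appears to mean that nothing outside the team's routine is done.

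The procedures are as follows:

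- **Performing Anesthesia:** propofol is given "to induce apnea in patients in both groups".
- **Data collect:** "The measurement will take place until the pulse oximetry is recorded at 95%. Assisted ventilation will then be instituted".
- **CPAP Realization:** saturation is read every 10 seconds and "recorded for a maximum time limit of five minutes in order to catch a minimum saturation of 95% in both groups". The next sentence says the attending anesthesiologist is present throughout and that management passes to that person's judgment once the study has ended.

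The background describes ordinary induction as apnea followed by ventilatory assistance from the anesthesiologist, usually by mask and bag. It also says: "Decreasing oxyhemoglobin saturation to levels less than or equal to 95% induces changes in hemodynamic parameters".

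**The concern.** The wait between the onset of apnea and the start of ventilation is the primary outcome (Time 1). Its length is set by the measurement, and the protocol describes no airway step in that interval that would account for it clinically. By the protocol's own account of usual practice, this departs from ordinary induction. By its own account of the 95% level, the departure ends at a saturation with physiological consequences. A statement that the study adds no risk therefore describes a property the design does not have.

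An ethics committee weighing a trial in ASA I or II preschool children needs an accurate account of what the research adds. A second, smaller issue is that the protocol gives both a time limit and a saturation trigger without saying how they relate.

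**Working it through.** **1. Reproduce the plan's own figure.** Inputs from Sample size: 166 ± 47 s (intervention), 131 ± 39 s (no intervention), 5% significance (taken as two-sided), 90% power.

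n per group = (47² + 39²) × (1.960 + 1.282)² / (166 − 131)² = 3730 × 10.51 / 1225 = 31.99, rounded up to 32. The total is 64, and 64 / 0.90 = 71.1, rounded up to the even number 72. Both stated figures reproduce. The sample size is not in dispute. The step confirms that these are the values the plan works with.

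**2. How many children would reach 95% before 300 s?** The means and SDs are from Sample size and the 300 s limit is from CPAP Realization. The distributional shapes are assumptions.

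Normal: P(T > 300) = 1 − Φ((300 − m)/s).
- CPAP: (300 − 166)/47 = 2.85, so P = 0.22%.
- Open: (300 − 131)/39 = 4.33, so P is below 0.001%.

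Lognormal: σ² = ln(1 + (s/m)²), μ = ln m − σ²/2, P(T > 300) = 1 − Φ((ln 300 − μ)/σ).
- CPAP: σ = 0.278, μ = 5.073, z = 2.27, so P = 1.2%.
- Open: σ = 0.291, μ = 4.833, z = 2.99, so P = 0.14%.

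| Group | Mean time to 95% | Reach 95% by 300 s, normal | Reach 95% by 300 s, lognormal |
|---|---|---|---|
| CPAP | 166 s | 99.8% | 98.8% |
| Open | 131 s | over 99.99% | 99.9% |

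With 36 per group, the expected number still above 95% at 300 s is 36 × 0.0022 + 36 × 0.000007 = 0.08 (normal), or 36 × 0.0116 + 36 × 0.0014 = 0.47 (lognormal). Either way it is fewer than 0.5 of 72.

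**3. Set the statements side by side.**

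| Topic | Background | Procedures | Ethical aspects |
|---|---|---|---|
| After apnea starts | Ventilatory assistance follows | Apnea is timed; ventilation follows the 95% reading | Nothing added by the study |
| Saturation of 95% or less | Hemodynamic changes | Endpoint of the timed interval | Nothing added by the study |

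The first two columns cannot both stand beside the third.

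**4. The two stopping statements.** The five-minute limit is worded as a limit on recording saturation. The start of ventilation is tied to the 95% reading. The only text bearing on a child above 95% at five minutes is the general sentence that management is discretionary once the study is over. Nothing says that reaching five minutes ends the study for that child.

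**The case against.** **The risk sentence may be about CPAP.** It goes on to say that no adverse effects contraindicating CPAP have been reported, so the authors may have had only the technique in mind. That may explain how the sentence arose, but as written it covers the whole study. Apnea with propofol may itself belong to ordinary induction, and this point does not depend on denying that. What is added is the wait for the 95% reading.

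**The five-minute limit and the 95% reading need not conflict.** A measurement endpoint and a maximum duration can coexist, and the discretion sentence offers a loose handover. This stands. A reader might infer that a child above 95% at five minutes has no provision at all, but the documents support only an ambiguity, and one expected to affect very few children.

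**The times are borrowed.** They are attributed to reference 20, which the background cites alongside reference 19 where it mentions other strategies such as apneic oxygenation. Whether the source matches this intervention, oxygen fraction or age group cannot be checked. This stands, so the percentages are conditional.

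**Stronger readings that the documents do not support:**

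- A reader might set the background's 4–10% desaturation during induction against the roughly 99% here. The background gives no saturation threshold for that figure, so the two are not comparable.
- A reader might infer that parents are misinformed. The consent form is not available for review, and Ethical aspects says it will set out the advantages and disadvantages of both techniques. The garbled sentence about routine procedures is weak evidence of what the form says.
- A reader might infer that the open group alone bears the risk. Both groups have induced apnea and the same trigger for ventilation, and on the planning figures the CPAP group has the longer interval (166 s against 131 s).
- The background sentence that appears to mention reduced heart function is broken in translation. Only the statement about hemodynamic change is relied on here.

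**Conclusion.** The statement that the study adds no risk is inconsistent with the protocol's procedures and with its own background, and it should be corrected. On the planning values, the research-driven interval averages 131 s (open) and 166 s (CPAP), and about 99% or more of children would reach 95% before 300 s. This assumes that the borrowed means and SDs apply to this population and that times are normal or lognormal. The inconsistency itself does not depend on those figures; they show only that it concerns nearly all participants.

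The relation between the five-minute limit and the 95% trigger is an ambiguity to be resolved, not a contradiction. The point concerns risk description and procedural clarity. It changes no estimate, sample size or analysis.

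**What to change.** - Reconcile the risk statement in Ethical aspects with the background, Performing Anesthesia, CPAP Realization and Data collect, so that it acknowledges the research-driven apnea interval and gives its expected duration, labelled as a planning assumption from the cited source.
- Check that the consent form agrees with the corrected statement, and clarify the sentence about routine procedures.
- Reconcile the recording limit in CPAP Realization and the ventilation trigger in Data collect into one consistent rule, and state when the study period ends for a child. Which rule applies is for the investigators and the ethics committee; none is proposed here.

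The cost is protocol wording, any consent wording that follows from the check, and an ethics notification. The downside is that some parents may decline once the interval is described plainly.
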